**12 STATISTICS**

The primary objective of this study is to assess the potential efficacy of RGI-2001. The primary endpoint for these purposes is grades II-IV acute GvHD, and the study subjects will be compared to a control group of subjects supplied by the CIBMTR. Control subjects will be chosen so as to meet all eligibility requirements for the clinical trial, have received a transplant in the same time window as the study subjects, and have been transplanted in a center that participates in this study.

[REDACTED]

[REDACTED]	[REDACTED]	[REDACTED]	[REDACTED]
[REDACTED]	[REDACTED]	[REDACTED]	[REDACTED]
[REDACTED]	[REDACTED]	[REDACTED]	[REDACTED]
[REDACTED]	[REDACTED]	[REDACTED]	[REDACTED]
[REDACTED]	[REDACTED]	[REDACTED]	[REDACTED]
[REDACTED]	[REDACTED]	[REDACTED]	[REDACTED]
[REDACTED]	[REDACTED]	[REDACTED]	[REDACTED]
[REDACTED]	[REDACTED]	[REDACTED]	[REDACTED]
[REDACTED]	[REDACTED]	[REDACTED]	[REDACTED]

Based on these estimates, it is anticipated that a total of 50 subjects who receive at least one dose of RGI-2001 will be enrolled, this including subjects from the run-in stage treated at the dose moved forward to the Expansion Phase. It is anticipated that a minimum of 250 subjects will be included in the control group.

**12.2 Demographics and Baseline Characteristics**

Categorical factors will be summarized with proportions, and continuous variables will be summarized using means and medians.

**12.3 Analysis Population, Handling of Dropouts, and Missing Data**

All subjects who receive at least one dose of RGI-2001 will be used for comparison to the CIBMTR subjects.

### 12.3.1 Analysis of Efficacy Data

The primary endpoint grades II-IV acute GvHD by Day 100 according to the MAGIC criteria will be compared between the study group and CIBMTR controls using logistic regression. The factors that will be considered for adjustment in this model include subject age, gender, donor age, type of donor (MRD, 8/8 URD 7/8 URD), source of allograft, diagnosis (AML, ALL, MDS, MPD including CMML), preparative regimen, GvHD prophylaxis regimen.

Secondary endpoints that will be modeled as binary outcomes will similarly be compared using logistic regression. Secondary endpoints that will be modeled as time-to-event outcomes will be compared using Cox regression.

Potential interactions of RGI-2001 and various factors will be examined by including appropriate factors into regression models.

Given that this is not a randomized study and that the intention is only to assess outcomes for a potential signal, no adjustments will be made for multiple comparisons. As such, a Type II error (or a false negative) is prioritized over a Type I error (or a false positive).

Binary exploratory outcomes will be summarized with proportions, continuous outcomes with means and medians, and time-to-event outcomes with Kaplan-Meier estimates or cumulative incidence estimates for endpoints with competing risks.

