## 2 PROTOCOL SYNOPSIS

Name of Sponsor	REGiMMUNE Corporation (JAPAN) [name]
Protocol Title	An Open Label, Non-Randomized Multicenter Phase 2b, Study with a Safety Run-in to Evaluate the Safety and Efficacy of RGI-2001 for the Prevention of Acute Graft- Versus-Host Disease Compared to Contemporary Controls in Subjects Following Allogeneic Hematopoietic Stem Cell Transplantation (alloHSCT)
Name of Investigational Product	RGI-2001
Protocol Number	RGI-2001-003
Phase	Phase 2
Indication	Prevention of Acute Graft-versus-Host Disease following alloHSCT
Study Centers	This study will be conducted at 8-12 sites in the United States.
Study Rationale:	Despite efforts to date, the incidence of acute GvHD remains high. Thus, improvements in the prevention of the disease constitutes a high unmet medical need.  Studies in both humans and mice have confirmed the pivotal role CD4+Foxp3+ Treg cells play in controlling GvHD ( Socié 2009 ). However, the development of Treg cell-based therapeutic modalities has been hampered, in part, by the small numbers of these cells. RGI-2001 is a liposomal form designed to deliver RGI-7000, which is an immunomodulatory compound that may promote the proliferation of Tregs in donor bone marrow and the development of tolerance to alloantigens and therefore constitutes a novel approach to the prevention of GvHD.
Objectives	Endpoints
Primary	

 
To assess the potential efficacy of RGI-2001 in addition to standard of care (SOC) vs SOC for the prevention of acute GvHD (aGvHD)
 
To characterize the safety and tolerability of 6 weekly intravenous (IV) infusions of
 
	
 
Efficacy: Grades II-IV aGvHD by Day 100 according to the Modified Keystone Criteria (Przepiorka 1995)
 
Safety: Incidence, nature, and severity of treatment-emergent AEs, SAEs, laboratory test values, vital-sign measures, and graft failure
 

RGI-2001 in subjects following alloHSCT
	

Secondary
	

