We consider a one-sided significance level of .10 to be sufficient evidence of a signal for moving forward.

[REDACTED]	[REDACTED]	[REDACTED]	[REDACTED]
[REDACTED]	[REDACTED]	[REDACTED]	[REDACTED]
[REDACTED]	[REDACTED]	[REDACTED]	[REDACTED]
[REDACTED]	[REDACTED]	[REDACTED]	[REDACTED]
[REDACTED]	[REDACTED]	[REDACTED]	[REDACTED]
[REDACTED]	[REDACTED]	[REDACTED]	[REDACTED]
[REDACTED]	[REDACTED]	[REDACTED]	[REDACTED]
[REDACTED]	[REDACTED]	[REDACTED]	[REDACTED]
[REDACTED]	[REDACTED]	[REDACTED]	[REDACTED]
[REDACTED]	[REDACTED]	[REDACTED]	[REDACTED]
[REDACTED]	[REDACTED]	[REDACTED]	[REDACTED]

Based on these estimates, it is anticipated that a total of 50 subjects who receive at least one dose of RGI-2001 will be enrolled, this including subjects from the run-in stage treated at the dose moved forward to the Expansion Phase. It is anticipated that a minimum of 250 subjects will be included in the control group.

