**Analysis of Efficacy Data**

The primary endpoint grades II-IV acute GvHD by Day 100 according to the Modified Keystone Criteria will be compared between the study group and CIBMTR controls using logistic regression. The factors that will be considered for adjustment in this model include subject age, gender, donor age, type of donor (MRD, 8/8 URD 7/8 URD), source of allograft, diagnosis (AML, ALL, MDS, MPD including CMML), preparative regimen, GvHD prophylaxis regimen.

Secondary endpoints that will be modeled as binary outcomes will similarly be compared using logistic regression.

Secondary endpoints that will be modeled as time-to-event outcomes will be compared using Cox regression.

Potential interactions of RGI-2001 and various factors will be examined by including appropriate factors into regression models.

Given that this is not a randomized study and that the intention is only to assess outcomes for a potential signal, no

adjustments will be made for multiple comparisons. As such, a Type II error (or a false negative) is prioritized over a Type I error (or a false positive).

Binary exploratory outcomes will be summarized with proportions, continuous outcomes with means and medians, and time-to-event outcomes with Kaplan-Meier estimates or cumulative incidence estimates for endpoints with competing risks.

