**5 STUDY OBJECTIVES AND ENDPOINTS**

Objectives	Endpoints
Primary	

 
To assess the potential efficacy of RGI-2001 in addition to standard of care (SOC) vs SOC for the prevention of aGvHD
 
To characterize the safety and tolerability of 6-weekly IV infusions of RGI-2001 in subjects following alloHSCT
 
	
 
Efficacy: Grades II-IV aGvHD by Day 100 according to the Modified Keystone Criteria (Przepiorka 1995)
 
Safety: Incidence, nature, and severity of treatment-emergent AEs, SAEs, laboratory test values, vital sign measures, and graft failure
 

Secondary	

 
To assess the potential efficacy of RGI-2001 in addition to SOC vs SOC for the prevention of chronic GvHD (cGvHD) according to the secondary endpoints listed
 
To assess the survival of subjects who received RGI-2001 in addition to SOC vs SOC
 
To evaluate the pharmacodynamics effects of weekly dosing of RGI-2001
 
	
 
Grades II-IV aGvHD by Day 180 according to the Modified Keystone Criteria
 
Total and moderate-severe cGvHD at 6 months and 1 year according to 2014 NIH criteria
 
Non-relapse mortality (NRM) rates at Day 100, 6 months and 1 year
 
Disease-free survival (DFS) at 6 months and 1 year
 
GvHD-free, relapse free survival (GRFS)a at 6 months and 1 year
 
Overall survival (OS) at 6 months and 1 year
 
Change from baseline in the percentage of CD4+CD25+CD45RA+ CD127-LO T cells (naive Tregs) on Days 14, 28, 42, 60, 100, 180
 

 
[REDACTED]
 
	
 
[REDACTED]
 

Objectives	Endpoints
	

• [REDACTED]

• [REDACTED]

a A GRFS event includes grade III-IV acute GVHD, chronic GvHD requiring systemic immunosuppressive treatment, disease relapse or progression, or death by any cause.

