2.3 Sample Size

As described in Section 12.1 of the protocol, the study plans to enroll and treat 50 subjects with RGI-2001. “Control” subjects who would have been eligible for this trial will be obtained from the CIBMTR and used for a non-randomized comparator group (details in a separate SAP).

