8.1 Acute GVHD

For the primary and secondary endpoints as well as certain exploratory endpoints, Keystone criteria will be used for the determination of the severity of aGVHD. For outcomes at a defined time points, the event time will be defined as the time from the “start date” of first RGI-2001 infusion (i.e., transplant date/Day 0) to the first date aGVHD is diagnosed with Keystone criteria Grades II-IV. The first date of aGVHD will be identified using the following eCRFs:

- Initial report: *aGvHD_d* eCRFs with Question 10 = II-IV (i.e., Keystone Grades)
- Maximum report: *aGvHDmax* eCRFs with Question 1 = II-IV (i.e., Keystone Grades)

The first diagnosis date across the eCRFs meeting the above criteria will be used to define the “event time” for this analysis. Censoring: Subjects who are alive without these events will be censored at the date of completion of the last aGVHD assessment, with follow-up truncated at 180 days. Subjects who die without aGVHD will be treated as competing-risk events. The occurrence of aGVHD as a function of time will be calculated using cumulative-incidence estimates.

As an exploratory outcome, MAGIC criteria will be used for the determination of the severity of aGVHD. Event time will be defined as the time from the “start date” of first RGI-2001 infusion to the first date aGVHD is diagnosed with MAGIC criteria Grades II-IV. The first date will be identified using the following eCRFs:

- Initial report: *aGvHD_d* eCRFs with Question 8 = II-IV (i.e., MAGIC Grades)
- Maximum report: *aGvHDmax* eCRFs with any of the following three categories:
 - Grade II: Stage 3 skin and/or stage 1 liver and/or stage 1 upper GI and/or stage 1 lower GI (questions 3,4,5, and 6 on the eCRF)
 - Grade III: Stage 2-3 liver and/or stage 2-3 lower GI, with stage 0-3 skin and/or stage 0-1 upper GI
 - Grade IV: Stage 4 skin, liver, or lower GI involvement, with stage 0-1 upper GI

The first diagnosis date across the eCRFs meeting the above criteria will be used to define the “event time” for this analysis. Censoring and competing-risk considerations will be the same as with the Keystone criteria (above). The occurrence of aGVHD as a function of time will be calculated using cumulative-incidence estimates.

Similar to above, the analysis will be repeated for Keystone and Magic separately using only Grades III and IV.

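### Protocol 12.3.1 tests the primary Day-100 endpoint on MAGIC grades; every other statement of that endpoint uses Modified Keystone, and SAP 8.1 makes MAGIC exploratory

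*Protocol*

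**What the plan says.** Two places in the supplied documents describe the model comparing treated subjects with CIBMTR controls, and they name different scales.

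- Protocol 12.3.1: "The primary endpoint grades II-IV acute GvHD by Day 100 according to the MAGIC criteria will be compared".
- Protocol synopsis, Analysis of Efficacy Data: "The primary endpoint grades II-IV acute GvHD by Day 100 according to the Modified Keystone Criteria will be compared".

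The endpoint definitions all side with the synopsis.

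- The synopsis objectives table reads "Efficacy: Grades II-IV aGvHD by Day 100 according to the Modified Keystone Criteria", and the tables in Protocol Section 5 and SAP 1.1 give the same Day-100 definition.
- The related secondary endpoint in Section 5 is "Grades II-IV aGvHD by Day 180 according to the Modified Keystone Criteria".
- SAP 8.1 states: "For the primary and secondary endpoints as well as certain exploratory endpoints, Keystone criteria will be used". It then gives MAGIC another role: "As an exploratory outcome, MAGIC criteria will be used for the determination of the severity of aGVHD".

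The synopsis (Statistical Considerations) sets the decision rule: "We consider a one-sided significance level of .10 to be sufficient evidence of a signal for moving forward". SAP 2.3 says control subjects will be "used for a non-randomized comparator group (details in a separate SAP"), and SAP 8.0 says its own methods leave the comparison out. That separate SAP is not among the documents supplied.

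**The concern.** Section 12.3.1 is the protocol body's account of the primary efficacy analysis. An analyst who follows it would test a MAGIC endpoint. That differs from the declared primary endpoint, from what SAP 8.1 estimates as primary in the treated group, and from the Keystone-graded Day-180 secondary endpoint.

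The study is open-label, has no randomised control, and makes no multiplicity adjustment. Which of two correlated results is held to the .10 rule should therefore be settled in writing before control outcomes are analysed.

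A related question, not a defect: the supplied text does not show which scale grades the controls. Protocol 9.4.6 points to Section 9.3 for both scales, but that text is absent here. Section 6 says treated-arm data capture resembles the CIBMTR's and names no scale.

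**Working it through.** **1. Is it a real conflict?** Both analysis sentences are current, legible text of the same protocol and are near-identical apart from the scale. Redaction and amendment history do not explain the difference. Section 12.3.1 is the only place that ties MAGIC to the primary endpoint.

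**2. Can the choice change who is an event?** Yes, by Protocol Appendices 2 and 3.

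| Feature | MAGIC (App. 2) | Modified Keystone (App. 3) |
|---|---|---|
| Upper-GI symptoms giving grade II | Persistent symptoms; footnote b sets duration, weight-loss or vomiting conditions; no histology in the staging | Histologic evidence required (footnote d) |
| Other documented cause, liver or gut | No one-stage downgrade; competing causes handled through confidence levels | Downgrade one stage (footnote c) |
| Diarrhoea | Volume or episode count | Volume only |
| Poor performance status | No rule | Grade IV possible with lesser organ involvement (footnote f) |

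The first two Keystone rules can make MAGIC read higher; the last can make Keystone read higher. The documents do not give the net direction or size.

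**3. Inputs.** From the documents: 50 treated, at least 250 controls, one-sided α = .10. Assumed, because the planning table is redacted: event rates of 35% treated and 50% control, and 2%, 5% or 10% of subjects graded on different sides of the cut. There is no legible power figure to reproduce. The test used here is an unadjusted two-proportion z test with pooled null variance; the plan uses covariate-adjusted logistic regression, so results are approximate.

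**4. Power with one scale in both groups.**

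- Pooled rate = (50×.35 + 250×.50)/300 = .475
- SE under the null = √(.475×.525×(1/50+1/250)) = .0774
- SE under the alternative = √(.35×.65/50 + .50×.50/250) = .0745
- Power = Φ((.15 − 1.2816×.0774)/.0745) = **.753**

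Shifting both groups together:

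| Shift (points) | −10 | −5 | −2 | +2 | +5 | +10 |
|---|---|---|---|---|---|---|
| Power | .784 | .764 | .756 | .750 | .748 | .750 |

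If MAGIC instead turns a fraction f of Keystone non-events into events in each group, the rates become .35 + .65f and .50 + .50f:

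| f | Treated v control | Power |
|---|---|---|
| 2% | 36.3% v 51.0% | .738 |
| 5% | 38.25% v 52.5% | .716 |
| 10% | 41.5% v 55.0% | .681 |

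**5. How often the two scales decide differently.** Multinomial simulation, 400,000 trials per case. Ranges cover discordance that is all MAGIC-only, split evenly, or all Keystone-only.

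| Discordant share | Disagree, 35% v 50% | Disagree, 50% v 50% | Either scale significant, 50% v 50% |
|---|---|---|---|
| 2% | .070–.072 | .039–.040 | .123 |
| 5% | .112–.114 | .061–.063 | .133–.135 |
| 10% | .154–.165 | .085–.089 | .144–.148 |

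Keystone alone rejects in about .103 of null trials.

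**6. A single trial near the boundary.** With controls at 125/250:

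- 20/50: difference .10, SE √(.4833×.5167×.024) = .0774, z = 1.29, p = .098
- 21/50: difference .08, SE .0774, z = 1.03, p = .151

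One reclassified treated subject changes the decision if controls do not move. If controls shift by the same 2%, 21/50 v 130/250 gives p = .098 and the decision stands. The risk lies in chance imbalance in reclassification, which step 5 averages over.

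**The case against.** The strongest reply is that the intent is obvious. All the endpoint tables say Modified Keystone, the synopsis analysis sentence says it, and SAP 8.1 assigns the roles expressly. Section 12.3.1 itself speaks of the primary endpoint, a term defined elsewhere as Keystone. On that reading one phrase was left uncorrected and there are not two live candidates. The intent is indeed clear, and the fix adopts it. But SAP 8.0 excludes the comparison from its scope, so the supplied text on the comparative test consists of two sentences that disagree.

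A second reply is that the separate CIBMTR SAP may already specify Keystone. It may. Protocol 12.3.1 would then contradict it on the primary endpoint and would still need correcting. The supplied SAP describes enrolment in the past tense, so alignment in the comparison SAP is the step with practical effect.

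A third reply concerns size. The event rates and discordance are assumed. No passage allows either result to be counted, so the inflated false-positive rate shows what an unsettled choice could cost and is not a property of the plan. The protocol also says it aims only at a signal and gives priority to avoiding false negatives. These limits stand; they temper the size and leave the contradiction in place.

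The supplied SAP cites protocol Version 2.0, and the supplied protocol's version cannot be confirmed. The conflict inside the protocol does not depend on that.

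**Conclusion.** Section 12.3.1 is wrong as written and should be corrected. It names a scale for the primary comparison that every other statement of the primary endpoint contradicts, and that SAP 8.1 reserves for an exploratory outcome.

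The effect on power is probably small: about 75%, staying at 75–78% under common shifts of up to 10 points and falling to 68% in the least favourable case examined. The material consequence is that the two scales can reach opposite conclusions on the .10 rule, in about 7% to 17% of trials with a 15-point effect and 4% to 9% with none. If either result could be claimed, the false-positive rate would rise from about 10% to 12–15%. All these figures rest on assumed event rates, assumed discordance and an unadjusted test.

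Confidence in the textual finding is high. Whether controls can be graded on Keystone remains an open question.

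**What to change.** 1. Confirm that the CIBMTR control forms support Modified Keystone grading.
2. In Protocol 12.3.1, replace MAGIC with Modified Keystone as the scale for the primary Day-100 comparison, so that it agrees with the synopsis, Section 5 and SAP 8.1.
3. Add two sentences there: *MAGIC grades II-IV is exploratory. The same scale is used for treated subjects and CIBMTR controls.*
4. Put the same wording in the separate CIBMTR SAP before control outcomes are analysed.

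The cost is low: one phrase and two sentences, repeated in the comparison SAP. SAP 8.1 shows that the treated-subject eCRFs already support both gradings, so no new treated-arm data are needed. If the control data do not support Keystone, more work is needed.

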### 7.5.2 *Subjects' Decision to Withdraw*

Subjects have the right to withdraw from the study at any time and for any reason without prejudice to their future medical care by the physician or at the institution.

Subjects can decline to continue receiving investigational product and/or other protocol-required therapies or procedures at any time during the study but continue participation in the study. If this occurs, the investigator is to discuss with the subject the appropriate process for discontinuation from investigational product or other protocol-required therapies and must discuss with the subject the options for continuation of the Schedule of Assessments and collection of data, including endpoints and adverse events. The investigator must document the level of follow-up that is agreed to by the subject (e.g., in person, by telephone/mail, through family/friends, in correspondence/communication with other physicians, from review of the medical records).

Withdrawal of consent from a study means that the subject does not wish to receive further protocol-required therapies or procedures, and the subject does not wish to or is unable to continue further study participation. Subject data up to withdrawal of consent will be included in the analysis of the study, and where permitted, publicly available data can be included after withdrawal of consent. The investigator is to discuss with the subject appropriate procedures for withdrawal from the study.

If a subject fails to return for scheduled visits, a documented effort must be made to determine the reason. If the subject cannot be reached by telephone after two attempts, a certified letter should be sent to the subject (or the subject's legally authorized representative, if appropriate) requesting contact with the Investigator. Attempts to contact the subject should be documented in the study records.

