4.3 Methods for Handling Missing Data

No imputations will be made for missing data, except as described for the time-to-event analyses in Section 4.1 (above).

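### The Day-100 logistic comparison with registry controls has no stated rule for subjects lost alive and aGvHD-free before Day 100; if such loss differs between groups, the one-sided .10 error rate shifts.

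*Protocol*

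**What the plan says.** Protocol 12.3.1, repeated in the synopsis, makes the primary endpoint a binary outcome by Day 100 that "will be compared between the study group and CIBMTR controls using logistic regression", adjusted for a list of patient, donor and transplant factors. The synopsis sets a one-sided .10 level as enough of a signal to go forward.

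Protocol 12.3 is headed as covering dropouts and missing data, but its only content is the analysis set: "All subjects who receive at least one dose of RGI-2001 will be used for comparison to the CIBMTR subjects". Protocol 7.5.2 adds that "Subject data up to withdrawal of consent will be included in the analysis of the study". Neither sentence says what value a subject with incomplete follow-up takes in a Day-100 model.

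For estimation, SAP 8.1 is explicit. "Subjects who are alive without these events will be censored at the date of completion of the last aGVHD assessment"; "Subjects who die without aGVHD will be treated as competing-risk events"; and "The occurrence of aGVHD as a function of time will be calculated using cumulative-incidence estimates". SAP 4.3 says "No imputations will be made for missing data, except as described for the time-to-event analyses", the exception being partial dates.

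SAP 2.3 and 8.0 place the comparison with CIBMTR controls in a separate SAP, which is not among the documents supplied.

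**The concern.** Take a subject last assessed, event-free, at Day 30. SAP 8.1 uses the 30 days and then censors. A plain logistic model cannot do that. It must record no aGvHD, although 70 days of risk were unobserved, or leave the subject out. The first choice pulls incidence down. The second pushes it up, because subjects who had aGvHD before leaving are kept while event-free leavers are removed.

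Equal distortion in both groups would largely cancel. Here the groups are followed through different systems. Treated subjects can withdraw consent, be withdrawn, or leave through an early-termination visit (Protocol 7.5). Controls are followed through CIBMTR forms on the registry's schedule (Protocol 11). Unequal early loss is therefore plausible. The coding could also be chosen after the open-label data have been seen. At stake are the error rate of the go-forward test with 50 treated subjects, and its agreement with the reported Day-100 incidence.

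**Working it through.** **Inputs from the documents.** 50 treated subjects, at least 250 controls, one-sided .10. The sample-size table is redacted, so the plan has no power figure to reproduce.

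**Assumptions.** True incidence p = 40% in both groups, inside the 25-70% background range spanned in Protocol 4.1.1. Onset is uniform over Days 14-80 (mean Day 47). A fraction c of a group is lost at a time uniform over Days 0-100, independent of outcome. The test is an unadjusted two-proportion z-test, standing in for the adjusted logistic model.

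**Step 1: effect on one group's incidence.** A subject who would drop out does so before onset with probability 47/100 = .47.
- Scored as non-event: p(1 − .47c). At c = .10: .40 × .953 = 38.1%.
- Lost alive and event-free: c(.47p + 1 − p) = .10 × (.188 + .600) = 7.9%.
- Excluded: .3812 / (1 − .0788) = 41.4%.

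**Step 2: effect on the test, 10% loss in the treated group only.**
- Non-event: pooled rate (50 × .3812 + 250 × .40)/300 = .397. Null SE = √(.397 × .603 × (1/50 + 1/250)) = .0758, so the test rejects below −1.2816 × .0758 = −.0971. The true mean difference is −.0188 with SE .0754. Error rate Φ((−.0971 + .0188)/.0754) = .149.
- Excluded: about 46.1 treated subjects at .4138, null SE .0786, cut-off −.1008, mean difference +.0138, SE .0789. Error rate Φ((−.1008 − .0138)/.0789) = .073.

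With the loss in the controls only, the same formulas give .064 (non-event) and .134 (excluded). With equal loss the mean difference is zero and the error rate stays at .10.

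**Step 3: simulation, same settings.**

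| Loss before Day 100 | Non-event | Excluded |
|---|---|---|
| None | .098 | .098 |
| 5% in both | .097 | .100 |
| 10% in both | .101 | .103 |
| 5% treated only | .122 | .086 |
| 10% treated only | .146 | .068 |
| 20% treated only | .214 | .048 |
| 5% controls only | .083 | .120 |
| 10% controls only | .063 | .136 |

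A separate simulation assumed 45% incidence, triangular onset (10, 30, 100 days) and 5% competing deaths. At 10% treated-only loss it gave .16 and .07. Its incidence shift checks by hand: mean onset (10 + 30 + 100)/3 = 46.7 days, so .45 × (1 − .0467) = 42.9%.

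**Step 4: censoring-aware estimate.** Aalen-Johansen incidence at Day 100 was run with 40% incidence, 5% deaths without aGvHD and 1,500 trials (simulation error about .008). The error rate was .109 with no loss, .113 with 10% treated-only loss and .106 with 10% control-only loss; mean differences in the last two were −.001 and .000. In that run the non-event and excluded codings gave .155 and .077 (treated only), and .056 and .136 (controls only).

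**Step 5: power.** For an assumed 25% versus 40% with 10% loss in both groups, power falls from .79 to .75 (non-event) or .77 (excluded).

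**Step 6: deaths.** A death before Day 100 without aGvHD is a non-event in the binary model and adds nothing to aGvHD cumulative incidence. The two approaches agree there.

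**The case against.** The strongest reply is that the comparison belongs to a separate SAP that may contain the rule. That stands. A reader might infer that the test and the reported incidence are known to rest on conflicting rules; the documents do not establish this. They show only that the supplied text states no rule. Protocol 12.3 is still the section on dropouts, and it neither gives the rule nor says where to find it.

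A reader might also infer that early dropout biases the test in any case. It does not: with equal loss the error rate was .097 to .103. Nor do the documents prescribe exclusion. The bar on imputation sits in a SAP that leaves the comparison out of its scope, while Protocol 12.3 uses all dosed subjects and 7.6 calls all dosed Expansion Phase subjects evaluable. Non-event coding is the more natural reading, and exclusion is a possible alternative.

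The plan also limits early loss: weekly visits to Day 42, then Days 60 and 100; encouragement to stay after stopping the drug; follow-up by telephone or records; and controls from participating centres. The shift is small in subjects: .40 − .3812 = 1.9 points, about one subject in 50. The trial seeks a signal and ranks false negatives above false positives. That does not settle the matter, because excluding lost treated subjects, or scoring lost controls as non-events, makes a benefit harder to detect.

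Finally, the simulations assumed independent dropout, which favours the censoring-aware method. If sicker subjects leave, that method can be biased too, and a censoring model fitted to a handful of treated dropouts is fragile.

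**Conclusion.** The point holds in a limited form. The stated primary model has no valid place for a subject lost alive and aGvHD-free before Day 100, and the supplied documents do not say what to do with one. Similar loss in both groups costs a little power and leaves the error rate near .10. Differential loss shifts the error rate, and the direction depends on which group loses subjects and which coding is used. At an assumed 10% loss it is about .15-.16 or .07 when only treated subjects are lost, and about .06 or .136 when only controls are lost. At 5% it ranges from about .08 to .12 in the 40% scenario.

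All loss rates, onset patterns and incidences here are assumptions, and the test is unadjusted. The gap justifies a change to the analysis text; it does not show that the trial's result will be biased.

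**What to change.** In Protocol 12.3.1 and the comparison SAP, make the primary comparison a regression on the cumulative incidence of Grade II-IV aGvHD at Day 100 that handles censoring. Inverse-probability-of-censoring-weighted logistic regression or pseudo-value regression would both serve. Treat death without aGvHD as a competing event, as in SAP 8.1, and keep the listed covariates and one-sided .10. Apply one censoring rule to both groups. Protocol 12.3 should state it or cite where it stands. Use the same method for Day-180 aGvHD if that is modelled as binary; 12.3.1 does not say whether it is.

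Keep plain logistic regression as sensitivity analyses, once with lost subjects as non-events and once with them excluded, and report early loss by group.

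The cost is wording, somewhat more analysis work with standard software, and reliance on censoring being independent given the covariates. With no censoring before Day 100 the weighted model equals the planned one.

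Separately, reconcile the grading system: Protocol 12.3.1 names MAGIC for the primary endpoint, while the synopsis and SAP 8.1 use the Keystone criteria.
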